6.2.8. Pharmacokinetics

For lorlatinib, concentrations will be summarized descriptively (n, mean, SD, CV, median, minimum, maximum, geometric mean and its associated CV) by cohort, cycle, day and nominal time. Individual patient and median profiles of the concentration-time data will be plotted by cohortcohortcycle and day (single dose and steady-state). For individual patient plots by time, the actual PK sampling time will be used. For summary statistics and mean/median plots by sampling time, the nominal PK sampling time will be used. MedianMedian profiles will be presented on both linear-linear and log-linear scales.

Presentations for concentrations will include but not be limited to:

- Listing of all concentrations of lorlatinib sorted by cohort, day of assessment, patient ID and nominal time post dose. The listing of concentrations will include the actual times. Deviations from the nominal time will be given in a separate listing.
- Summary of concentrations by cohort, day of assessment and nominal time post dose, where the set of statistics will include n, mean, standard deviation, coefficient of variation (CV), median, minimum, maximum, geometric mean and its associated CV and the number of concentrations above the lower limit of quantification.

- Linear and semi-log plots of median concentrations against nominal time post dose by cohort, day of assessment (based on the summary of concentrations by day of assessment and time post dose).
- Linear plots of individual concentrations against actual time post dose by cohort and day of assessment.
- Trough concentrations will be plotted using a box-whisker plot by cohort, cycle and day in order to assess the attainment and maintaining of steady-state.

Plasma pharmacokinetic parameters of lorlatinib on Day 1 of Cycle 1 (C1D1) and at steady state including the maximum plasma concentration (C_{max}), time to maximum plasma concentration (T_{max}), area under the plasma concentration versus time profile from time 0 to time t (AUC_t) and area under the plasma concentration versus time profile within a dose interval (AUC_{tau}) for lorlatinib will be estimated using non-compartmental analysis. If data permit or if considered appropriate, area under the plasma concentration versus time curve to infinity (AUC_{inf}), terminal elimination half-life ($t_{1/2}$), oral plasma clearance (CL/F), apparent volume of distribution (V_z/F) and accumulation ratio (R_{ac}) will be also estimated. The C1D1 and steady-state PK parameters will be summarized descriptively by cycle and day and will include the set of summary statistics as specified in the table below:

Parameter	Summary Statistics
AUC_{last} , AUC_{inf}^* , AUC_{tau} , C_{max} , CL/F^* , V_z/F^* ,	N, arithmetic mean, median, cv%, standard deviation, minimum, maximum, geometric mean, geometric cv%.
T_{max}	N, median, minimum, maximum.
$t_{1/2}$, R_{ac}^*	N, arithmetic mean, median, cv%, standard deviation, minimum, maximum.

* if data permits.

Pharmacokinetic and Exposure-Response Analysis

Pharmacokinetic and pharmacodynamics data from this study may be analyzed using compartmental or mixed-effect modeling approaches and may also be pooled with other study results. PK/PD modeling may be attempted to investigate any causal relationship between lorlatinib exposure and efficacy, CCI or significant safety endpoints. The results of these analyses, if performed, will be reported separately.

CCI

CCI

6.4. Baseline and Other Summaries

6.4.1. Baseline Summaries

- **Demographic and Physical Characteristics**

The following demographic and baseline characteristics will be summarized by number and percentage:

- Gender(male, female);
- Age <(18-<45; 45- <65; ≥65) >;
- Eastern Cooperative Oncology Group (ECOG) Performance status;
- Smoking classification (never smoker, former smoker, smoker).

Age (continuous), height (cm), weight (kg) will be summarized with descriptive statistics (mean, median, standard deviation, minimum, and maximum).

- **Disease Characteristics**

The following baseline disease characteristics will be summarized by number and percentage:

- Histopathological Classification TMN stage at initial diagnosis and current stage;
- Extent of disease (locally/advanced, metastatic);
- Measurable disease at baseline (yes/no) (see [Section 5.2.8](#));
- Adequate baseline assessment (yes/no) (see [Section 5.2.11](#));
- Involved tumor sites at baseline.

Time since diagnosis (months), defined as (date of first dose– date of diagnosis)/30.4375, will be summarized by descriptive statistics (mean, median, standard deviation, minimum, and maximum).

Involved tumor sites at baseline will be derived from target and non target lesions at baseline. Each patient will be counted once per organ. Similarly, number of sites of disease at baseline will be derived by counting the number of unique organ sites from target and non target lesions at baseline. “Other” will be counted as one organ site.

- **Medical History**

- Medical history will be coded using the most current version of MedDRA and summarized by MedDRA’s System Organ Class (SOC) and PT. Each patient will be counted only once within each PT or SOC. Summaries will be ordered by primary SOC and PT in descending order of frequency by Cohort. Separate summaries will be provided for past and present conditions.

- **Prior Anti-Cancer Treatments**

Prior anti-cancer treatments include systemic therapy, radiation, and surgery.

The number and percentage of patients in each of the following anti-cancer therapy categories will be tabulated:

- Patients with at least one type of prior anti-cancer treatment; Patients with different type of previous ALK inhibitor;
- Patients with at least one prior anti-cancer drug therapy;
- Patients with at least one prior anti-cancer radiotherapy;
- Patients with at least one prior anti-cancer surgery.

Prior anti-cancer drug therapy will be summarized as follows based on the number and percentage of patients:

- Number of prior anti-cancer therapy regimens: 0 / 1 / >1;
- Intent of Therapy: Neo-Adjuvant/Adjuvant/Advanced – Metastatic.

6.4.2. Study Conduct and Subject Disposition

The following analyses will be based on the FA population overall and separately by Cohort.

6.4.2.1. Patient Disposition

A summary of the number of patients enrolled by site will be provided by Cohort as well as overall for the FA population.

Discontinuations from study treatment will be summarized using the SA set.

Discontinuations from study treatment due to adverse events will be identified as either related or not related to study treatment. If causality is missing the event will be considered related to treatment. If multiple events lead to study treatment discontinuation and at least one was considered related, discontinuation will be reported as related to study treatment.

6.4.2.2. Protocol Deviations

Protocol deviations will be compiled prior to database closure and will be listed and summarized by category (n(%)) for the FA set by Cohort. Categories will be assigned by the study Clinician.

6.4.3. Study Treatment Exposure

The following analyses will be based on the SA population.

6.4.3.1. Exposure to lorlatinib

The summary of treatment exposure for lorlatinib will include the following information:

- Treatment duration (weeks);
- Cumulative dose (mg);
- Dose intensity (mg/week);
- Relative dose intensity (%);

The duration of lorlatinib (in weeks) is defined as:

$$\text{Treatment duration (weeks)} = (\text{last dose date} - \text{first dose date} + 1)/7$$

The cumulative dose (mg) of lorlatinib is the sum of the actual dose levels that the patient received (ie, total dose administered (mg)). Lorlatinib is given once daily, administered as 4 x 25 mg oral tablets, continuously; therefore if all doses (eg, d mg/day) were received in a week the cumulative dose would be 7x 100 mg.

The dose intensity (DI) and the relative dose intensity (RDI) of lorlatinib will be calculated for each patient during the study. The DI (mg/week) of lorlatinib during the study is defined as

$$\text{DI (mg/week)} = [\text{cumulative dose (mg)}]/[\text{treatment duration (weeks)}]$$

The RDI of lorlatinib is defined as the ratio of the DI and planned dose intensity and expressed in %

$$\text{RDI (\%)} = 100 \times [\text{DI (mg/week)}]/[7 \times 100 \text{ (mg/week)}].$$

6.4.3.2. Dose Reductions, Interruptions, and Delays

A dose reduction is defined as a non-zero dose that is less than the prior dose.

The number and percentage of patients with at least one dose reduction as well as a breakdown of dose reductions (1/2/3) will be summarized by Cohort.

Reasons for dose reductions will also be summarized. Patients can contribute to more than one reason if multiple dose reductions occurred for different reasons, but will only be counted once per reason. Percentages will be calculated based on the total number of patients in SA set.

An interruption is defined a 0 mg dose administered for more than 1 day. The number and percentage of patients with dose interruptions and the corresponding reasons will be summarized by Cohort. Patients can contribute to more than one reason if multiple dose interruptions occurred for different reasons, but will only be counted once per reason. Percentages will be calculated based on the total number of patients in the SA set.

What follows defines how dose interruptions will be counted in the case of considerations for multiple dose interruptions:

- If an interruption occurs consecutively for at least two days due to the same reason, then it will be counted only once.
- If an interruption occurs consecutively for at least two days due to different reasons, then it will be counted for each reason.
- If an interruption occurs for more than one day due to the same reason, but the days are not consecutive, ie, there is at least one dosing day in between, then each dose interruption will be counted as a different occurrence.

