Table 2. Lorlatinib Dose Modifications for Lorlatinib-Related Toxicities

Toxicity	Grade 1**	Grade 2**	Grade 3	Grade 4
Non-Hematologic Toxicities				
Pancreatitis	NA	
If elevated enzymes (both amylase and lipase are Grade ≤ 2) are observed in the absence of radiological findings of pancreatitis: continue lorlatinib at the same dose level without dose hold. Repeat lipase and amylase and obtain pancreatic isoenzyme if possible.
 
If radiologically confirmed pancreatitis: withhold lorlatinib dose. Repeat radiology and lipase and amylase weekly and obtain pancreatic isoenzyme. If appropriate, resume lorlatinib treatment at one dose level lower if radiology has returned to baseline and lipase and amylase are Grade ≤ 2.
	Permanently discontinue lorlatinib	Permanently discontinue lorlatinib

Table 2. Lorlatinib Dose Modifications for Lorlatinib-Related Toxicities

Toxicity	Grade 1**	Grade 2**	Grade 3	Grade 4
Pneumonitis (in the absence of disease progression, pulmonary embolism, positive cultures or radiation effect) section	Asymptomatic, radiographic findings only: No need for lorlatinib dose adjustment. Initiate appropriate monitoring.	Withhold current lorlatinib dose until toxicity has returned to baseline. Rule out infection and consider initiating treatment with corticosteroids. Then resume lorlatinib treatment at one dose level lower. Discontinue lorlatinib permanently if pneumonitis recurs or if failure to recover after 6 weeks of study treatment hold and steroid treatment.	Permanently discontinue lorlatinib	Permanently discontinue lorlatinib
Electrocardiogram QTc prolongation (see Section 5.5.2)	Assess electrolytes and concomitant medications Correct any electrolyte abnormalities, or hypoxia Continue lorlatinib at the same dose level	Assess electrolytes and concomitant medications Correct any electrolyte abnormalities, or hypoxia Continue lorlatinib at the same dose level	Withhold lorlatinib dose Assess electrolytes and concomitant medications Correct any electrolyte abnormalities, or hypoxia. Upon recovery to Grade ≤ 1 resume lorlatinib treatment at one dose level lower.	Permanently discontinue lorlatinib
LV Dysfunction	CTCAE v4.03 does not report Grade 1.	CTCAE v 4.03 does not report Grade 2	Permanently discontinue lorlatinib	Permanently discontinue lorlatinib

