Non-Hematologic General	Continue lorlatinib at the same dose level	Continue lorlatinib at the same dose level	Withhold lorlatinib dose until toxicity is Grade ≤ 1 (or has returned to baseline) then reduce the dose by 1 level or rechallenge at the same dose*	Withhold dose until toxicity is Grade ≤ 1 (or has returned to baseline), then reduce the dose by 1 level* or discontinue at the discretion of the investigator

Table 2. Lorlatinib Dose Modifications for Lorlatinib-Related Toxicities

Toxicity	Grade 1**	Grade 2**	Grade 3	Grade 4

* Subjects who develop asymptomatic Grade 4 hyperuricemia or Grade 3 hypophosphatemia may continue lorlatinib without dose modification at the discretion of the investigator. Nausea, vomiting or diarrhea must persist at Grade 3 or 4 despite maximal medical therapy to require lorlatinib dose modification.
 
** In cases where no specific dose adjustments for Grade 1 or Grade 2 treatment-related toxicity are provided, investigators should always manage their patients according to their medical judgment which may include dose reduction or interruption based on the particular clinical circumstances.
 
Section If a subject has a potential diagnosis of pneumonitis or drug-related lung injury the same evaluations/procedures provided in Section 5.5.3 should be considered to assist or exclude the diagnosis of pneumonitis during this period.
				
Hematologic Toxicities				
Hematologic General	Continue lorlatinib at the same dose level	Continue lorlatinib at the same dose level	Withhold lorlatinib dose until toxicity is Grade ≤1 (or has returned to baseline), then rechallenge at the same dose or reduce the dose by 1 dose level	Withhold lorlatinib dose until toxicity is Grade ≤1 (or has returned to baseline), then rechallenge at the same dose or reduce the dose by 1 dose level
Lymphopenia	Continue lorlatinib at the same dose level	Continue lorlatinib at the same dose level	If no evidence of infection or other clinically significant toxicity, continue lorlatinib at the same dose; otherwise, withhold dose until toxicity is Grade ≤1 (or baseline) then rechallenge at the same dose or reduce by 1 level	If no evidence of infection or other clinically significant toxicity, continue lorlatinib at the same dose; otherwise, withhold dose until toxicity is Grade ≤1 (or baseline) then rechallenge at the same dose or reduce by 1 level

Table 2. Lorlatinib Dose Modifications for Lorlatinib-Related Toxicities

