CNS effects ^b	Continue lorlatinib at the same dose or withhold dose until recovery to baseline. Then resume at the same dose or reduce by 1 dose level	Withhold dose until toxicity is less than or equal to Grade 1. Then resume at 1 reduced dose level	Withhold dose until toxicity is less than or equal to Grade 1. Then resume at 1 reduced dose level	Permanently discontinue lorlatinib
^b Examples of CNS effects could include changes in speech, memory, sleep, cognition, or vision.				

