5.2.4. Definition of Cycle and Cycle Day

Cycle start and end dates are derived per patient.

Lorlatinib is administered every 3 weeks in a cycle; therefore the nominal cycle length is 21 days.

For Cycle X, the actual cycle start date for each subject is the earliest start date of dosing (dose>0 at that visit) in Cycle X visit CRF exposure page.

- For all but the last cycle;
- Actual cycle stop date is calculated as the start date of the next cycle minus one day.
- Actual cycle duration is calculated from Day 1 of a cycle to the day prior to Day 1 of the next cycle, as follows:

$$\text{Actual Cycle Duration (weeks)} = (\text{cycle stop date} - \text{cycle start date} + 1) / 7$$

- For the last cycle, actual cycle duration is calculated as follows:

$$\text{Actual Cycle Duration (weeks)} = (\text{last date of study treatment} - \text{cycle start date} + 1) / 7$$

The cycle day will be calculated as:

$$\text{Cycle day} = \text{Date of the assessment/event} - \text{cycle start date} + 1.$$

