6.5.1. Adverse Events

All analyses will be based on treatment emergent events unless otherwise specified. Treatment emergent is defined in [Section 3.5.1](#). AEs not considered treatment emergent will be flagged in data listings.

A high level summary of adverse events will include the number and percent of patients with:

- Any Adverse Event;
- Serious AE;
- Adverse Events with CTCAE Grade 3-4;
- Grade 5 events;
- AEs leading to dose interruptions;
- AEs leading to dose reductions;
- AEs leading to withdraw.

Additionally, the number of any AE will be provided. Each unique adverse event at the PT level in each Cohort of the study for a patient is included in the count.

Seriousness, toxicity grade, action taken (interruption, reduction, and withdraw) are as reported by the investigator on the adverse event CRF.

Summaries by Cohort, SOC and PT in decreasing frequency based on the frequencies observed in each Cohort will be provided for:

- Treatment Emergent Events by Maximum Toxicity Grade (All Causality);
- Treatment Emergent Events by Maximum Toxicity Grade (Treatment Related);
- Serious Treatment Emergent Events (All Causality);
- Serious Treatment Emergent Events (Treatment Related).

An event will be considered treatment related if the investigator considered the event related to the study drug or this information is unknown.

The following summaries will be provided by Cohort and PT/clusters of AEs (ie, summaries will not include SOC) in decreasing frequency based on the frequencies observed in the study treatment for:

- Treatment Emergent Events (All Causality) by Preferred Term (including Clusters of Preferred Term) and Maximum Toxicity Grade;
- Treatment Emergent Events (Treatment Related) by Preferred Term (including Clusters of Preferred Term) and Maximum Toxicity Grade;
- Treatment Emergent Grade 3-5 Events (All Causality) by Preferred Term (including Clusters of Preferred Term) and Maximum Toxicity Grade;
- Treatment Emergent Adverse Events Leading to Dose Interruptions by Maximum Toxicity Grade (All Causality);
- Treatment Emergent Adverse Events Leading to Dose Reductions by Maximum Toxicity Grade (All Causality);
- Treatment Emergent Adverse Events Leading to Permanent Withdraw by Maximum Toxicity Grade (All Causality);
- Serious Treatment Emergent Events (All Causality).
- Serious Treatment Emergent Events (Treatment Related).

Each patient will be counted only once within each PT.

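### Read literally, the SAP's dose-reduction rule does not count a lower dose resumed after a hold, the usual route to a lower dose in Protocol Tables 2 and 3

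*SAP*

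**What the plan says.** SAP 6.4.3.2 gives the counting rule: "A dose reduction is defined as a non-zero dose that is less than the prior dose". In that sentence the non-zero condition is attached to the current dose only. The same section describes a hold as a dose: "An interruption is defined a 0 mg dose administered for more than 1 day".

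The rule feeds three outputs in SAP 6.4.3.2, each given separately for the two cohorts: the patient count and the breakdown ("The number and percentage of patients with at least one dose reduction as well as a breakdown of dose reductions (1/2/3) will be summarized by"), and a summary of the reasons for reductions.

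Elsewhere the SAP excludes zero doses explicitly. SAP 5.2.4 takes the cycle start as "the earliest start date of dosing (dose>0 at that visit) in Cycle X visit CRF exposure page". No such filter is attached to the prior dose in 6.4.3.2.

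Protocol 5.5, Table 2, often reaches a lower dose by way of a hold:

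- CNS effects, Grades 2 and 3: "Withhold dose until toxicity is less than or equal to Grade 1. Then resume at 1 reduced dose level".
- Pneumonitis, Grade 2, after withholding: "Then resume lorlatinib treatment at one dose level lower".
- General non-hematologic toxicity, Grade 3, after withholding: "then reduce the dose by 1 level or rechallenge at the same dose".

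SAP 6.5.1 tabulates AEs leading to dose reduction from a different source: "Seriousness, toxicity grade, action taken (interruption, reduction, and withdraw) are as reported by the investigator on the adverse event CRF".

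**The concern.** If a hold is a 0 mg dose, it is also the dose that precedes the restart. No positive dose is less than 0 mg, so no restart after a hold can qualify as a reduction, however much lower it is than the dose before the hold. The rule would then miss the sequence that the protocol's dose-modification tables most often describe.

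What is at stake is descriptive, but it belongs to a stated secondary objective, safety and tolerability. The loss would also be selective. Reductions for Grade 2 or 3 CNS effects, which Table 2 routes through a hold, would drop out, and SAP 3.5.2 names CNS events as adverse events of special interest. Lipid-driven reductions, for which Table 2 states no hold immediately beforehand, would stay in. A study report could list a patient under AEs leading to dose reduction and show the same patient as never reduced in the exposure table.

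**Working it through.** The documents state no number or rate of reductions for this study, so there is no figure to reproduce. The check applies the rule to example sequences.

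**Inputs.** Dose levels of 100, 75 and 50 mg (Protocol 5.5, Table 1). A hold is 0 mg (SAP 6.4.3.2).

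**Rules.** Let d(t) be the dose on record t.

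- Literal rule: record t is a reduction if d(t) > 0 and d(t) < d(t−1).
- Last non-zero rule: record t is a reduction if d(t) > 0 and d(t) < d(s), where s is the latest earlier record with d(s) > 0.

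**Results.**

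| Dose sequence (mg) | Literal | Last non-zero |
|---|---|---|
| 100 → 75 | 1 | 1 |
| 100 → 0 → 75 | 0 | 1 |
| 100 → 0 → 75 → 0 → 50 | 0 | 2 |
| 100 → 0 → 75 → 50 | 1 | 2 |
| 100 → 0 → 50 | 0 | 1 |
| 100 → 0 → 100 | 0 | 0 |
| 100 → 0 → 100 → 75 | 1 | 1 |
| Daily records: 14 days at 100, 7 at 0, 14 at 75 | 0 | 1 |

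In the second row, 75 < 0 is false and 75 < 100 is true. The fourth row affects the breakdown rather than the patient count: the patient is counted, but under one reduction instead of two.

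**Direction.** If the literal rule counts record t, then 0 < d(t) < d(t−1). So d(t−1) is itself non-zero and is the last non-zero dose, and the second rule counts the record too. The literal rule can therefore only miss reductions; it cannot add any.

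**How often the protocol's route passes through a hold.** Nine rows of Table 2 can lead to a lower dose.

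- In seven, the lower dose comes directly after withholding: pancreatitis (Grade 2, radiologically confirmed), pneumonitis (Grade 2), QTc prolongation (Grade 3), general non-hematologic (Grades 3 and 4), general hematologic (Grades 3 and 4), lymphopenia (Grades 3 and 4) and CNS effects. In some of these the lower dose is an option beside restarting at the same dose.
- In the other two, cholesterol and triglycerides, Grade 4 leads to a hold and a restart at the same dose. The lower dose comes only on recurrence, with no hold stated immediately before it. That is the sequence 100 → 0 → 100 → 75, counted under both rules.
- In Table 3 (Protocol 5.5.2), every reduction follows a hold.

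**The case against.** The SAP says prior dose, not immediately prior dose. The protocol uses dose for an assigned level that survives a hold: when Tables 2 and 3 speak of resuming at the same dose or one level lower, they compare with the dose before the hold. The SAP describes itself as a supplement to the protocol, so a programmer could well read the prior dose as the last level taken, with the non-zero condition there only to keep interruptions out of the count. The CRF layout is not shown either, so we do not know whether a hold is a separate 0 mg row. This stands, and it is why the point concerns what the rule yields when read literally, not what the tables will certainly show. It does not remove the point. The favourable reading adds a qualifier that the sentence gives only to the current dose, the same section calls a hold a 0 mg dose, and SAP 5.2.4 shows that the SAP excludes zero doses expressly where it wants to.

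A reader might go further and infer from the earlier lorlatinib study (Protocol 1.2.3.4) that the table would show about 0% in place of 22.7%. The documents do not support that, for three reasons.

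- The 22.7% is the share of patients with AEs associated with dose reductions. Its counterpart here is the AE-action summary in SAP 6.5.1, which the definition in 6.4.3.2 does not touch.
- Reductions without an immediately preceding hold still count: lipid recurrence (Table 2), the start of a strong CYP3A inhibitor (Protocol 5.9.1), and reductions by investigator judgement at Grades 1 and 2 where no specific adjustment is given. Hypercholesterolemia (83.7%) and hypertriglyceridemia (65.8%) were the most frequent treatment-related AEs in that study.
- Its 31.9% with AEs associated with temporary discontinuations is given without the overlap with the 22.7%, so no share of reductions after a hold can be derived.

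**Conclusion.** The definition should be corrected. Taken literally, it misses every lower dose resumed directly after a hold, and the error runs in one direction only. The outputs at risk are the three in SAP 6.4.3.2: patients with at least one reduction, the 1/2/3 breakdown and the reasons. They could also disagree with the AE-action summaries in SAP 6.5.1.

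This rests on two assumptions: that holds enter the exposure data as 0 mg records, and that the prior dose is programmed as the preceding record. If either fails, the counts come out right despite the wording.

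The size cannot be stated, because the share of reductions that follow a hold is not given. Nor do the documents support the broader inference that the trial's tolerability results as a whole would look too favourable. Cumulative dose, dose intensity and relative dose intensity (SAP 6.4.3.1) reflect every hold and every lower dose, and the AE-action tables are independent of the rule. The primary endpoint, the hypothesis test, the sample size and all other efficacy results are untouched.

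**What to change.** In SAP 6.4.3.2, replace *the prior dose* in the definition with *the most recent prior non-zero dose*. Under that wording 100 → 0 → 75 mg counts once and 100 → 0 → 100 mg does not count, as intended.

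The cost is one phrase in the SAP and one comparison in the program, with no new data. If the sponsor already meant the last non-zero dose, no result changes. The edit alters a counting rule only and leaves every dosing instruction in the protocol as it is. It should be made before the exposure tables are programmed.
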